4.5.10.12.1 Roche HD Mobile Application: In-Clinic Assessments

Patients will be instructed to bring the smartphone and wearable to every clinic visit to check adherence and technical status of the devices. Every 16 weeks, when clinical ratings will occur, patients will be asked to conduct the In-Clinic Assessments ("Full active test") under the supervision of trained site staff, with the exception of the EQ-5D-5L, which will be completed on the electronic device at the site. Patients should be instructed to not complete the Roche HD mobile app EQ-5D-5L on days that coincide with the study drug administration visit.

The smartphone and wearable must be returned to the clinic in cases where the patient does not meet eligibility criteria, at the end of the study, or upon early termination from the study.

4.6 TREATMENT, PATIENT, STUDY, AND SITE DISCONTINUATION

4.6.1 Study Treatment Discontinuation

Patients must permanently discontinue study treatment if they experience any of the following:

- Any medical condition that the investigator or Sponsor determines may jeopardize the patient's safety if he or she continues to receive study treatment
- Investigator or Sponsor determination that treatment discontinuation is in the best interest of the patient
- Pregnancy

The primary reason for study treatment discontinuation should be documented on the appropriate eCRF. Patients who discontinue study treatment prematurely will not be replaced.

Patients will return to the clinic for an end-of-treatment visit and safety follow-up visit (if applicable) after the final dose of study drug (see [Appendix 1a](#) and [Appendix 1b](#) for additional details).

4.6.2 Patient Discontinuation from Study

Patients have the right to voluntarily withdraw from the study at any time for any reason. In addition, the investigator has the right to withdraw a patient from the study at any time. Reasons for withdrawal from the study may include, but are not limited to, the following:

- Patient withdrawal of consent

- Study termination or site closure
- Loss of capacity to consent, if legal guardian consent is not possible

Note: Withdrawal of patients who lose capacity to consent is a requirement in Germany.

Every effort should be made to obtain information on patients who withdraw from the study but have not withdrawn consent. The primary reason for withdrawal from the study should be documented on the appropriate eCRF. If a patient requests to be withdrawn from the study, this request must be documented in the source documents and signed by the investigator. Patients who withdraw from the study will not be replaced.

4.6.3 Study Discontinuation

The Sponsor has the right to terminate this study at any time. Reasons for terminating the study may include, but are not limited to, the following:

- The incidence or severity of AEs in this or other studies indicates a potential health hazard to patients
- Patient enrollment is unsatisfactory

The Sponsor will notify the investigator if the Sponsor decides to discontinue the study.

4.6.4 Site Discontinuation

The Sponsor has the right to close a site at any time. Reasons for closing a site may include, but are not limited to, the following:

- Excessively slow recruitment
- Poor protocol adherence
- Inaccurate or incomplete data recording
- Non-compliance with the International Council for Harmonisation (ICH) guideline for Good Clinical Practice
- No study activity (i.e., all patients have completed the study and all obligations have been fulfilled)

5. ASSESSMENT OF SAFETY

5.1 SAFETY PLAN

RO7234292 is not approved and clinical development is ongoing. The safety plan for patients in this study is based on clinical experience with RO7234292 in completed and ongoing studies. Safety risks for the LP procedure and RO7234292 are outlined below in Sections 5.1.1 and 5.1.2, respectively. Please refer to the RO7234292 Investigator's Brochure for a complete summary of safety information.

Several measures will be taken to ensure the safety of patients participating in this study, including the eligibility criteria. Patients will undergo safety monitoring during the study, including assessment of the incidence and severity of AEs. Guidelines for managing AEs, including criteria for treatment interruption or discontinuation, are provided below.

5.1.1 Known Risks Associated with Lumbar Puncture

Post-lumbar puncture syndrome, spinal hematoma, and meningitis (see Sections 5.1.1.1–5.1.1.3) are potential risks associated with LP.

In the completed Phase I/IIa study, the most commonly reported AEs across all treatment groups (RO7234292, N=34; placebo, N=12) were procedural pain (54% of patients) and post-LP syndrome (37% of patients).

In the recently completed Phase II OLE Study BN40697, potential LP procedure-associated selected AEs were reported with similar incidence across the cohorts despite the difference in dosing frequency (16 patients [69.6%] in the Q4W cohort and 17 patients [73.9%] in the Q8W cohort). Overall, the most frequently reported event was procedural pain (41.3%). In the ongoing Phase III Study BN40423, patients enrolled under Protocol Versions 1–3 (receiving Q4W blinded treatment) were discontinued following discontinuation of the Q4W dosing. These patients' treatment assignments are now unblinded and hereby referred to as original design cohort (ODC). In the ODC, potential LP procedure associated selected AEs were reported with similar incidence across the three cohorts (17 patients [47.2%] in the placebo cohort, 14 patients [40%] in the Q4W cohorts, and 17 patients [47.2%] in the Q8W cohort). Overall, the events reported with highest incidence were procedural pain and post-lumbar puncture syndrome (14% each).

As of 07 August 2020, in the ongoing Study BN40955, potential LP procedure associated selected AEs were reported in 30 patients [22.9%] in the Q8W cohort and 11 patients [15.1%] in the Q16W cohort. Overall the most frequently reported event was procedural pain (9.2% in the Q8W cohort and 4.1% in the Q16W cohort). Many of the complications associated with LP can be avoided by the mandatory use of a 24G atraumatic needle with a stylet, adherence to procedural guidelines (see LP manual and instructional video), and careful assessment of the patient, including neurologic examination with fundoscopy both prior to and post-LP procedure. Lumbar puncture should be avoided when a contraindication is present.

Cerebrospinal fluid leakage is more likely with larger bore needles. To minimize this risk, a 24G atraumatic needle will be used. Training for use of the 24G atraumatic needle in this study will be provided prior to initiation of LP, as will a review of extension tubing use and the need to gently aspirate CSF for timely collection. If headache with characteristics of low-pressure syndrome is present after the procedure and persists despite standard of care treatment, a blood patch should be considered. Formation of a subarachnoid epidermal cyst (i.e., when a skin plug is introduced into the arachnoid

space) can be avoided by use of a needle with stylet, which is mandatory. Rarely, brain herniation can occur in the setting of LP and increased intracranial pressure.

There are specific contraindications to performing LP. These include unstable cardiorespiratory status, where positioning patient for LP may not be tolerated, signs of cerebral herniation or incipient cerebral herniation, signs of increased intracranial pressure, or focal neurological findings on examination. In those patients, LP (and IT treatment administration) should not be performed and appropriate diagnostic work-up should be initiated. On a case-by-case basis and following discussion with the Medical Monitor, such patients may be able to resume treatment.

In the setting of HD, for the purposes of LP and IT bolus injection of RO7234292, moderate to severe truncal chorea may also be prohibitive.

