4.5.3 Physical and Neurologic Examinations

A complete physical examination, performed at specified visits (see [Appendix 1a](#) and [Appendix 1b](#)), should include an evaluation of the head, eyes, ears, nose, and throat, and the cardiovascular, dermatologic, musculoskeletal, respiratory, gastrointestinal, and neurologic systems; genitourinary examinations may be performed if clinically indicated. The physical examinations should be conducted in the same manner on each occasion to ensure comparability to previous examinations, including weight at each visit. Height will be obtained from the preceding study. For patients required to undergo screening, height will be collected at screening only.

A neurologic examination, including fundoscopy, performed at screening (patients required to undergo screening only), inclusion and at every clinical visit, should include assessment of mental status, level of consciousness, cranial nerve function, motor function, sensory function, reflexes, gait, and coordination (see [Appendix 12](#)). The neurologic examinations should be conducted in the same manner on each occasion to ensure comparability to previous examinations. Neurologic examinations should be performed before and after treatment on each dosing day, *or before the lumbar puncture, if there is no study treatment administration.*

Any abnormality identified at screening (patients required to undergo screening only) and baseline (inclusion visit) should be recorded on the General Medical History and Baseline Conditions eCRF. Changes from baseline abnormalities should be recorded in patient notes. New or worsened clinically significant abnormalities (i.e., beyond expected variation; normal age-related change; or HD-related clinical progression) should be recorded as AEs on the Adverse Event eCRF.

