Among events associated with the central nervous system in Study BN40697, dysarthria was reported in 2 patients in the Q4W cohort; coordination abnormal was reported in 1 patient in the Q4W cohort; pleocytosis was reported in 1 patient in the Q4W arm; and ataxia was reported in 1 patient each in the Q4W and Q8W cohorts, respectively. An SAE of cerebrovascular accident was reported in 1 patient in the Q4W cohort, which was considered not related to study drug by the investigator. SAEs of hemiparesis, myelitis, and neuritis (SUSAR cases) were reported in another patient in the Q4W cohort. In Study BN40423 ODC, ataxia (SUSAR case) and dysarthria were reported in 1 patient each in the Q4W cohort. In Study BN40955, treatment-emergent event of ataxia was reported in 1 patient each in the Q8W and Q16W cohorts, respectively, pleocytosis was reported in 1 patient in the Q8W cohort, and two neurological SUSAR cases were reported in 2 patients in the Q8W cohort (1 patient each for arachnoiditis and aseptic meningitis). For details see the RO7234292 Investigator's Brochure. Following LP administration and post-LP mobilization, neurologic examinations should be conducted. In addition, patients should be observed in-clinic for any complications or complaints post-LP and IT bolus injection of RO7234292.

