Appendix 2b Visit Schedule for the First 2 Years of Study Participation While on Treatment Pause

Month	0	1	2	3	4	5	6	7	8	9	10	11	12	13	14	15	16	17	18	19	20	21	22	23	24
Week	1	5	9	13	17	21	25	29	33	37	41	45	49	53	57	61	65	69	73	77	81	85	89	93	97^a
Q8W ^{b, c}	LP	P	NLP ^d	P	LP	P	NLP ^d	P	LP	P	NLP ^d	P	LP		NLP ^d		LP		NLP ^d		LP		NLP ^d		LP
Q16W ^e	LP	P	CV	P	LP	P	CV	P	LP	P	CV	P	LP		P		LP		P		LP		P		LP

CV=non-treatment clinic visit; P=phone call; Q8W=every 8 weeks; Q16W=every 16 weeks; LP=clinic visit with lumbar puncture; NLP= clinic visit without lumbar puncture

Notes: The non-treatment clinic visit includes collection of the following assessments during the first year of assignment to Q16W regimen: vital signs, neurologic examination, hematology, chemistry, pregnancy test, urinalysis, concomitant medications, and adverse events.

^a All patients should continue performing the corresponding visits as described in [Appendix 2b](#) beyond the first 2 years.

^b Q8W=patients randomized to Q8W and paused from receiving RO7234292 study drug following the USM-DIL (dated 22 March 2021).

^c Patients who were randomized to Q8W study drug administration and paused from receiving RO7234292 study drug will continue to undergo clinic visits performing LP and alternate non LP (NLP) visits. At the LP visits, CSF sample for safety/biomarkers will be performed. Local PT and/or INR, aPTT, Platelet count and neurological examinations will be performed prior to LP only. CSF sample for PK and plasma for PK will not be required after study treatment was paused. Immunogenicity samples will continue to be collected.

^d Non-LP visits will continue as described in [Appendix 1a](#) and [Appendix 1b](#). CSF samples for PK/safety/biomarkers and local PT/and/or INR, aPTT and platelet count are not required at these visits. Neurological examinations should be performed at Non-LP visits.

^e Q16W=patients randomized to Q16W and paused from receiving RO7234292 study drug following the USM-DIL (dated 22 March 2021)..

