Appendix 12 Guidance for Neurological Examination

Perform the neurological examination in the same way every time at screening and at every clinic visit. At dosing visits, perform examination predose and postdose after the participant has walked for 30 minutes post-drug injection.

Neurological Examination

- Mental status (appearance, level of consciousness, behavior, speech)
- Cranial Nerves II (including Visual Acuity and Fundoscopy)–XII
- Motor examination (bulk, tone, and strength)
- Coordination
- Abnormal movements
- Gait
- Reflexes
- Sensation (vibration, light touch, pin prick/temperature)

Note: The neurological examination should be followed at the non-dosing clinic visits, end-of-treatment visit, and safety follow-up visit. *At visits when a lumbar puncture is performed without study treatment administration, the neurological examination should be performed prior to the lumbar puncture.*

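### Drug-free lumbar punctures during the dosing pause have no scheduled post-procedure neurologic examination, and if dosing does not resume most fall outside the adverse-event reporting period

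*Combined protocol and SAP*

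**What the plan says.** LPs continue every 16 weeks for all patients while dosing is paused, for CSF safety and biomarker samples (Appendix 1a footnote s, Appendix 1b footnote u, Appendix 2b).

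**Examination.** Section 5.1.1, which covers risks of the LP itself, includes "neurologic examination with fundoscopy both prior to and post-LP procedure" in its list of ways to avoid complications. Section 4.5.3 has the examination done before and after treatment on dosing days, "or before the lumbar puncture, if there is no study treatment administration". Appendix 1a footnote l and Appendix 1b footnote j repeat this. Appendix 2b footnote c says for the Q8W arm that "neurological examinations will be performed prior to LP only"; footnote e, for Q16W, is silent. Appendix 12 says: "At visits when a lumbar puncture is performed without study treatment administration, the neurological examination should be performed prior to the lumbar puncture".

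**AE reporting.** Sections 5.3.1 and 5.4.2.2 end AE and SAE reporting 5 months after the final dose. After that, Section 5.6 asks only for SAEs believed related to earlier study drug, and footnotes bb (Appendix 1a) and z (Appendix 1b) add all deaths. Before the first dose, Section 5.3.1 makes SAEs caused by a protocol procedure reportable and names the LP as an example. The protocol does not say whether the last dose before the pause is the final dose.

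**The concern.** The LP is the main invasive procedure left in the study, and patients remain on study for safety follow-up. The section on LP risk expects an examination on both sides of the procedure, and the schedule provides one side. A site working from the schedule will not do the other.

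Section 5.1.1.2 says spinal hematoma can show itself through new sensory or motor symptoms, which the Appendix 12 examination tests. In Appendix 2b, after Week 49 a Q16W patient's next contact after an LP is a phone call 8 weeks later and the next clinic visit is 16 weeks later. A same-day post-LP examination would be the only scheduled in-person check in that interval.

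The AE period is tied to the last dose, while the procedure that carries the risk goes on. A non-fatal LP complication judged unrelated to drug, even a serious one, could then occur at a protocol procedure without having to be reported.

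**Working it through.** **1. Examination timing at a drug-free LP**

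| Place | Before LP | After LP |
|---|---|---|
| Section 5.1.1 | yes | yes |
| Section 4.5.3 | yes | not named |
| Appendix 1a footnote l; Appendix 1b footnote j | yes | not named |
| Appendix 2b footnote c (Q8W) | yes | excluded |
| Appendix 2b footnote e (Q16W) | silent | silent |
| Appendix 12 | yes | second examination tied to dosing visits |
| Section 4.5.5 | – | postdose examination only, where applicable |
| Section 5.1.2.8 | each visit | dosing days only |

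In footnote c, the restriction to pre-LP cannot mean LP visits only, because footnote d requires examinations at non-LP visits too. It refers to timing within the LP visit. So no text schedules a post-LP examination at a drug-free LP in either arm.

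Size: 52/16 = 3.25 drug-free LPs per patient-year, each with one scheduled examination where Section 5.1.1 implies two. Before the pause, the postdose examination took place 52/8 = 6.5 times a year in Q8W and 3.25 times in Q16W.

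**2. AE period against LP dates** (assuming dosing does not resume and the last pre-pause dose is the final dose)

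- Five calendar months from a last dose between 1 November 2020 and 22 March 2021 is 150, 151 or 153 days: 150/7 = 21.4 to 153/7 = 21.9 weeks.
- Last dose at an LP week (Q16W, or Q8W at Weeks 1, 17, 33 and so on): drug-free LPs at +16, +32 and +48 weeks.
- Last dose at a non-LP week (Q8W at Weeks 9, 25, 41 and so on): drug-free LPs at +8, +24 and +40 weeks.
- The second drug-free LP is therefore due at 24 weeks (168 days) or 32 weeks (224 days), after the period has closed. In each series, 2 of the 3 LPs in the first 52 weeks fall outside it, as do all later ones.
- Visit windows: 24 − 1 − 1 = 22 weeks = 154 days, still past 153. A further 7-day re-dosing delay gives 21 weeks = 147 days, inside the period. An early end-of-treatment LP could also fall inside. Hence normally, not always.

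**3. What the LP event rates can and cannot show**

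- BN40423 original design cohort, LP-associated AEs: "17 patients [47.2%] in the placebo cohort" and the same count on Q8W. 17/0.472 = 36 per cohort. The difference is 0, with 95% half-width 1.96 × √(2 × 0.472 × 0.528/36) = 0.231, or about 23 percentage points either way.
- This study, LP-associated AEs: "30 patients [22.9%] in the Q8W cohort and 11 patients [15.1%] in the Q16W cohort" (30/0.229 = 131; 11/0.151 = 73). Post-LP syndrome: 7/131 = 5.3% and 2/73 = 2.7%.
- All are cumulative per-patient rates with injections being given. None is a rate per drug-free LP.

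**The case against.** The strongest reply is that the schedule is deliberate and uniform. The amendment rationale states the pre-LP rule, it is carried through five places, and Section 4.5.5 makes the postdose examination conditional. Section 5.1.1 is risk narrative with no visit schedule, so sites face little practical doubt. This stands. It makes the mismatch an unreconciled inconsistency rather than an oversight in the schedule. It does not remove the mismatch: the same amendment revised Section 5.1.1 and left the before-and-after wording in place, and the documents give no reason for omitting the post-LP examination.

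A reader might infer that Section 5.1.2.1 is a second conflicting instruction, since it says "Following LP administration and post-LP mobilization, neurologic examinations should be conducted". The documents do not support that. It sits under drug risks, its next sentence asks that "patients should be observed in-clinic for any complications or complaints post-LP and IT bolus injection of RO7234292", and Sections 4.5.5 and 5.1.2.8 tie this pairing to dosing. It most likely concerns dosing LPs.

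On AE reporting, dosing is described as paused, so no final dose can be identified while the pause is open. Follow-up runs to study completion, the schedule collects AEs at every visit and call, and Section 5.4 lists SAEs as reportable whatever their relation to drug. The conditional nature of the point stands. The other provisions do not close the gap, because Section 5.4.2.2 and footnotes bb and z put the 5-month limit on that same reporting.

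It is also fair that no missed event is shown. Procedural pain is the most frequent event overall in this study, most post-LP syndrome events were mild or moderate and non-serious, spinal hematoma is described as very rare, and a same-day examination would miss later onset.

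**Conclusion.** The point holds in two parts, as a change worth making at the next amendment.

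(a) Section 5.1.1 and the operative schedule disagree about the post-LP examination at drug-free LPs, about 3.25 per patient-year in both arms. This part needs no assumption about whether dosing resumes. Which way to reconcile the texts is the sponsor's decision.

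(b) If dosing does not resume and the last pre-pause dose is the final dose, AE reporting normally closes before the second drug-free LP. Two of the first three such LPs, and all later ones, then fall outside it. Non-fatal LP complications judged unrelated to drug would not be reportable, although an LP-caused SAE before first dose would be.

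A reader might take the equal 47.2% rates on placebo and Q8W to show that drug-free LPs in this study carry the same risk as dosing LPs. They do not. They come from a blinded Q4W-injection cohort, accumulate over patients rather than procedures, and leave a difference of about 23 points in either direction open. This is a low-cost safeguard, not an urgent hazard, and no endpoint analysis depends on it.

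**What to change.** **Examination.** In Section 4.5.3, Appendix 1a footnote l, Appendix 1b footnote j, Appendix 2b footnotes c and e, and Appendix 12, state: *At LP visits without study treatment, perform the neurologic examination before the LP and again after the post-LP walk.* Remove the pre-LP-only restriction on the examination from footnote c. If the sponsor prefers to keep the pre-LP rule, it should limit the before-and-after wording in Section 5.1.1 to dosing LPs and give the reason.

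**AE reporting.** In Sections 5.3.1, 5.4.2.2 and 5.6 and footnotes bb (Appendix 1a) and z (Appendix 1b), state: *AEs and SAEs attributed to a protocol LP are reported for as long as study LPs continue, and through the safety follow-up visit after the last LP, regardless of time since the last dose.* This extends the principle Section 5.3.1 already applies before first dose. Also state whether the last pre-pause dose counts as the final dose.

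**Cost.** About 3.25 extra examinations per patient-year, no more than the postdose examinations done before the pause, at visits already attended and with no new visit or equipment. Each is a full Appendix 12 examination including fundoscopy, so staff time is not nil. The reporting change adds a modest amount of AE reporting at contacts already scheduled; the documents give no basis for a workload figure.

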5.1.1.1 Post–Lumbar Puncture Syndrome

RO7234292 is delivered directly to the CNS by IT LP injection. Post–LP syndrome (e.g., headaches, nausea, vomiting, infection, hemorrhage, nerve irritation pain) can occur with IT administration. Experience to date with post–LP syndrome, as reported in the completed Phase I/IIa study, includes headache, which occurred after 10% of procedures and was transient and mild in the vast majority of patients.

In the recently completed Phase II OLE Study BN40697, post-LP syndrome events (such as post-LP syndrome, headache, migraine, nausea, vomiting or procedural headache) occurring within 5 days of LP were reported in 9 patients (39.1%) in the Q4W cohort and 13 patients (56.5%) in the Q8W cohort.

In the Study BN40423 ODC, post-LP syndrome events (post-LP syndrome, headache, migraine, nausea, vomiting or procedural headache) occurring within 5 days of LP were reported in 14 patients (38.9%) in the placebo cohort, 8 patients (22.9%) in the Q4W cohort and 14 patients (38.9%) in the Q8W cohort.

As of August 2020, in the ongoing Study BN40955, post-LP syndrome events (such as post-LP syndrome, headache, migraine, nausea, vomiting or procedural headache) occurring within 5 days of LP were reported in 7 patients (5.3%) in the Q8W cohort and 2 patients (2.7%) in the Q16W cohort.

The majority of these events were mild or moderate and non-serious. No events led to treatment interruption or discontinuation.

Patients should walk post–LP, (see Section 4.3.2.1). However, if a patient develops a headache after the LP with characteristic features, which makes walking intolerable, the patient should be encouraged to first sit down and if the headache persists then the patient should lie in a comfortable position, which is most likely in the supine position owing to the postural nature of the symptoms. Supportive treatment may include

rehydration, consumption of caffeinated drinks, simple analgesics, opioids, and antiemetics. If these conservative measures fail, more specific measures may be indicated.

